4.4 EFFICACY ANALYSIS

All efficacy analyses will be based on the modified intent-to-treat populations defined in Section 4.1.2. The primary and secondary endpoints will be analyzed as change scores, calculated as follows:

Outcome measure change score = (post-baseline value – baseline value)

In the above determination of change score for CDR-SB and RBANS, the baseline value will be defined as the average of all non-missing values before the first dose of study drug, which should be an average of the screening and baseline values. For all other cognitive and biomarker endpoints, baseline value will be defined as latest observed value before the first dose of study drug.

For the primary and secondary endpoints, mean changes from baseline will be compared across treatment arms using mixed-models for repeated measures (MMRM). Each model will have an intercept term, a term for baseline value of the endpoint, a term for APOE4 strata (carrier vs. non-carrier), a term for dementia status strata (pAD vs. mAD), an interaction term of the two stratification factors, categorical visit terms, a term for treatment group, a term for baseline age, and terms for treatment-by-visit interactions. This will be implemented using SAS proc mixed syntax similar to the excerpt below:

```
proc mixed data=data;  
class PATNUM VISIT TRT APOE4 DEMSTATUS;  
model var = BASE BAGE APOE4 DEMSTATUS APOE4*DEMSTATUS VISIT TRT TRT*VISIT  
/solution noint ddfm=kr;  
repeated VISIT / subject=PATNUM type=UN;  
lsmeans VISIT*TRT / pdiff cl alpha=0.05;  
estimate 'MTAU9937A vs Placebo Wk 73' TRT -1 1/cl;
```

An unstructured variance-covariance matrix for within-subject errors will be assumed. If the unstructured covariance structure matrix results in a lack of convergence, the heterogeneous Toeplitz covariance structure followed by the heterogeneous first-order autoregressive

covariance structure will be used. In these cases, the sandwich estimator will be used to get the variance of the treatment effect estimator.

If model assumptions are violated (e.g. large deviations from normality of residuals), alternative modeling strategies including data transformations, permutation-based approaches, and/or robust mixed effects modeling methodology (Koller, Journal of Statistical Software 2016) will be used as appropriate for additional sensitivity analyses.

Comparisons of Interest

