Comparisons of efficacy will be performed between each MTAU9937A treatment arm and the placebo group by first pooling data from the middle and high doses for the first statistical test of the primary endpoint and then subsequently testing each treatment arm individually. Thus, there will be four comparisons across the doses:

MTAU9937A dose groups for hierarchical testing:

- **Group 1:** MTAU9937A 4500 mg + MTAU9937A 8100 mg vs placebo
- **Group 2:** MTAU9937A 4500 mg vs placebo
- **Group 3:** MTAU9937A 8100 mg vs placebo
- **Group 4:** MTAU9937A 1500 mg vs placebo

One model pooling middle and high doses will be used to test the Group 1 hypothesis. A second model including all 3 active arms separately will be used for Groups 2-4.

Type I Error Management

Type I error for the primary endpoint will be controlled using a fixed sequence testing procedure at the two-sided 5% significance level. The testing procedure will proceed with comparisons following the order across the four dose groups detailed above. After the first hypothesis test, each subsequent hypothesis will only be formally tested if the preceding one is significant at the 5% level.

For each dose group that has a significant result for the hypothesis test for the primary endpoint, a separate fixed sequence testing procedure will be ungated for that dose group's secondary endpoints that will similarly proceed at the 5% level. The overall testing procedure is detailed visually in the table below.

		MTAU9937A Dose group			
Endpoint		Group 1	Group 2	Group 3	Group 4
Primary	Change in CDR-SB score from baseline to Week 73				
Secondary	1. Change in ADAS-Cog13 score from baseline to Week 73	↓	↓	↓	↓
	2. Change in ADCS-ADL score from baseline to Week 73	↓	↓	↓	↓
	3. Change in RBANS total score from baseline to Week 73	↓	↓	↓	↓
	4. Change in Amsterdam iADL score from baseline to Week 73	↓	↓	↓	↓

No control for type I error will be applied for the exploratory endpoints, including sensitivity, subgroup, and biomarker analyses. Efficacy analyses will not involve formal comparisons between the MTAU9937A treatment arms.

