4.4.1 Primary Efficacy Endpoint

The primary efficacy objective for this study is to evaluate the efficacy of MTAU9937A compared with placebo on the basis of CDR-SB change from baseline at Week 73 (with baseline defined as the average of available measurements before first dose which is expected to include both screening and baseline values).

The estimand of interest (the mITT estimand) is the mean absolute difference in CDR-SB change from baseline at Week 73 between active drug and placebo. It will be estimated using all randomized patients who received at least one dose of study drug, regardless of adherence to the assigned study treatment or to the protocol.

The MMRM approach described in Section 4.4 should provide a reasonable estimate of the mITT estimand. Mean change from baseline will be estimated at each post-baseline timepoint for each study arm (placebo and each treatment arm) using least squares means and 95% confidence intervals. The absolute difference in mean change from baseline will be estimated for each treatment arm compared with placebo using least-squares mean estimates from the MMRM model along with 95% confidence intervals.

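### The SAP's ESTIMATE line labelled Week 73 omits the Week 73 treatment-by-visit coefficients, so it does not return the Week 73 difference and cannot supply the three Group 2–4 contrasts

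*SAP*

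**What the plan says.** SAP section 4.4 specifies an MMRM and gives example code. The model statement is "model var = BASE BAGE APOE4 DEMSTATUS APOE4*DEMSTATUS VISIT TRT TRT*VISIT", with VISIT and TRT both in the CLASS statement. Two later lines produce treatment comparisons: "lsmeans VISIT*TRT / pdiff cl alpha=0.05" and then "estimate 'MTAU9937A vs Placebo Wk 73' TRT -1 1/cl". The code is introduced with "This will be implemented using SAS proc mixed syntax similar to the excerpt below".

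The target is set in section 4.4.1: the estimand "is the mean absolute difference in CDR-SB change from baseline at Week 73 between active drug and placebo". The same section says that the differences from placebo are obtained "using least-squares mean estimates from the MMRM model along with 95% confidence intervals".

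Under Comparisons of Interest, Group 1 (4500 mg and 8100 mg pooled) has its own model. For the rest, "A second model including all 3 active arms separately will be used for Groups 2-4", so TRT has four levels there. The type I error text adds: "Efficacy analyses will not involve formal comparisons between the MTAU9937A treatment arms".

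**The concern.** With a treatment-by-visit interaction in the model, a contrast on the treatment main effect alone is not a comparison at any one visit. The line labelled as the Week 73 contrast therefore appears to compute something other than its label. A line with two coefficients also cannot serve a four-level treatment factor without further specification.

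The fixed-sequence procedure opens with one Week 73 p-value for Group 1. That p-value gates every later dose comparison, and each dose group's own primary p-value opens its secondary sequence. The ESTIMATE line is the only line in the excerpt singled out by name as the treatment contrast. A programmer who followed the label would obtain either no estimate or a visit-averaged effect reported as the Week 73 result.

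**Working it through.** **Inputs.** Model terms and the ESTIMATE coefficients: SAP 4.4. Visits at Weeks 25, 49 and 73: SAP 4.4.3. For power, SAP 2.2: true difference 0.6, SD 2, 25% dropout, 228 pooled active and 137 placebo before dropout, alpha 0.05. The two-sided level is stated under Type I Error Management.

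**1. The SAP's own power figure.** After dropout, n = 228 × 0.75 = 171 and 137 × 0.75 = 102.75. The standard error is 2 × √(1/171 + 1/102.75) = 0.2496, and 0.6/0.2496 = 2.403. Two-sided power is 67.1% by the normal approximation and 66.8% by the noncentral t. The SAP states 68%, so the figure reproduces and refers to the Week 73 difference.

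**2. What the contrast should be.** Let τ be the treatment effects and γ the visit-by-treatment effects. At Week 73 the difference between active (A) and placebo (P) is

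(τ_A − τ_P) + (γ_73,A − γ_73,P).

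The VISIT term and the covariates cancel. The ESTIMATE line contains only the first bracket.

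**3. Estimability.** The no-intercept design was built with every term in the model statement, for 2, 3 and 4 treatment levels and for 3 and 4 visits. Four visits were included because the CDR row of the schedule in Protocol Appendix 1 appears to carry a mark at Week 69. A contrast L is estimable if L = L X⁻X. All six layouts agreed:

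| Coefficients | Estimable? | Quantity |
|---|---|---|
| `TRT -1 1`, interaction at zero | No | – |
| `TRT -1 1`, interaction spread evenly | Yes | Difference averaged over visits |
| `TRT -1 1` plus −1, 1 on the Week 73 interaction cells | Yes | Week 73 difference |

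Having Week 73 as the last visit does not rescue the line, because a contrast with zero interaction coefficients is still not estimable.

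**4. Four treatment levels.** Here `-1 1` means (−1, 1, 0, 0): only the first two levels are compared, and the SAP does not state their order. If placebo and then 1500 mg come first, the line addresses Group 4 only, the last test in the sequence. If the doses come in ascending order with placebo last, it compares 4500 mg with 1500 mg, an active-versus-active comparison of the kind the SAP rules out.

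**5. Size of the discrepancy.** The documents give no time course, so these are illustrations with a true Week 73 effect of 0.6:
- linear growth: (0.2 + 0.4 + 0.6)/3 = 0.40
- linear growth with Week 69 as a fourth visit: (0.2 + 0.4 + 0.567 + 0.6)/4 = 0.44
- constant effect: 0.60

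**6. Power of the averaged contrast (Group 1, linear growth).** The SD of a three-visit average is √(sum of all entries of the covariance matrix)/3. With SD 2 at every visit and between-visit correlation ρ it is 2 × √((1 + 2ρ)/3): 1.461 at ρ = 0.3 and 1.932 at ρ = 0.9. Using n = 171 and 102.75 throughout, noncentral t:

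| ρ (assumed) | 0.3 | 0.5 | 0.7 | 0.9 |
|---|---|---|---|---|
| SD 2 at every visit | 59% | 50% | 43% | 38% |
| SD proportional to time (0.67, 1.33, 2) | 89% | 82% | 75% | 70% |

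Against 67% for the Week 73 contrast, power can move either way.

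**The case against.** The code is explicitly illustrative and uses placeholder names. The line directly above the ESTIMATE line requests visit-by-treatment least-squares means with differences, p-values and limits, which gives the correct Week 73 comparison for every arm. The prose fixes the timepoint at Week 73, names least-squares-mean differences, and says which model serves which group. On this view one faulty line is overridden by the text around it. The two-level form is a generic template placed before the four comparisons are set out, and an active-versus-active result would require someone to run it unchanged and ignore its label.

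The power figures rest on assumed time course, correlation and SD, and they apply the full 25% dropout from the first visit. With dropout spread evenly over the three intervals and partial data used, the ranges become 45–65% (constant SD) and 78–91% (SD proportional to time).

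Most of this stands as a limit on consequence. The primary analysis does not fail, and the power figures show neither a direction nor a dependable size of harm. It does not make the line correct. Code that is to be followed in similar form should not carry a contrast that contradicts its own label and the estimand. The LSMEANS request prints every pairwise cell difference: with three visits, 6 cells give 6 × 5/2 = 15 for two treatment levels, and 12 cells give 12 × 11/2 = 66 for four. The SAP does not say in so many words which output supplies the test.

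**Conclusion.** The concern holds. Under the model as written, the ESTIMATE line is either not estimable or a visit-averaged difference, and it is not the Week 73 difference as labelled. In the four-level model it can address at most one of the three Group 2–4 pairs. This follows from the model statement alone and needs no assumption about the data.

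The size of the discrepancy does depend on an assumed time course. The contrast would target 0.40 rather than 0.60 under linear growth over three visits, with no discrepancy if the effect is constant. The intended analysis is recoverable from the LSMEANS line and section 4.4.1, so this is a code correction that should be made before unblinding, not a failure of the primary analysis.

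**What to change.** Either delete the ESTIMATE line or replace it with one contrast per dose group that includes the Week 73 interaction coefficients, with the TRT level order stated. For two levels with placebo first, visits 25/49/73 and the excerpt's CLASS order, the coefficients are `TRT -1 1 TRT*VISIT 0 0 0 0 -1 1`. The four-level model needs three lines, each with −1 on placebo and +1 on one dose, on both TRT and the Week 73 interaction cells. For the Group 1 model, also say whether the 1500 mg arm stays in as a third level, because that changes the coefficient list.

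Add one sentence: the Week 73 least-squares-mean difference from the MMRM supplies the estimate, confidence interval and p-value for each of Groups 1–4, including the pooled Group 1 test.

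The cost is a correction to the code excerpt and one sentence in the SAP. The model, the two-model approach, the testing sequence, the stated power and the data collected are unaffected.

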3.3 RATIONALE FOR STUDY DESIGN

3.3.1 Rationale for MTAU9937A Dose and Schedule

The potentially efficacious dose of MTAU9937A is not known. Due to the lack of a fully translatable animal model of AD, preclinical experiments do not provide guidance for human efficacious dose selection. In addition, the exploratory PD and efficacy data collected in the Phase I study (GN39058) were not intended to guide dose selection. Therefore, this study will evaluate three doses of MTAU9937A in order to explore dose/exposure-response relationships for efficacy, pharmacodynamics, safety, and tolerability.

The rationale for the three proposed dosing regimens of 1500, 4500, and 8100 mg Q4W in this study take into account the safety profiles from the nonclinical toxicology studies, safety and PK profiles from the Phase I study (GN39058), and results from the target engagement modeling exercise. The 8100-mg IV Q4W dose, the highest dose level of MTAU9937A, is justified on the basis of a 1.3- to 1.4-fold safety margin between the highest mean exposure (based on both C_{max} and AUC) in the multiple-dose portion of the Phase I study and the predicted steady-state exposure in this study at the 8100-mg dose. The favorable safety profile of MTAU9937A to date in Study GN39058 supports

doses up to 8100 mg IV (see Section 1.2.2). In addition, simulations incorporating model-based PK variability predict that these three doses will have minimal overlap with regard to PK exposure.

In the target engagement modeling analysis, simulations were conducted to predict percent target (i.e., tau) engagement by MTAU9937A in the interstitial fluid of the brain. Results demonstrated that high target engagement (i.e., > 80%) is predicted for the three doses under various scenarios (e.g., several plasma:brain partitioning ratios and MTAU9937A binding affinities). It should be noted that the extent of target engagement required for clinical efficacy is unknown.

The dosing frequency will be Q4W, except during the first month, when a dose of MTAU9937A will also be administered to patients on Week 3 to rapidly increase the serum concentrations to those achieved at steady state.

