2.2 DETERMINATION OF SAMPLE SIZE

This study enrolled 457 patients randomized to one of three active IV dose arms or to an IV placebo dose arm in a 2:3:2:3 ratio. This sample size provides reasonable precision for estimating a clinically significant treatment effect on CDR-SB scores when MTAU9937A is compared with placebo. Assuming an observed 0.6-point difference in mean CDR-SB decline between the 4500 mg MTAU9937A arm and placebo at Week 73 (a 40% relative reduction in decline versus placebo), a standard deviation across patients of 2, and a 25% dropout rate, a 90% confidence interval on the population treatment effect point estimate for the CDR-SB is approximately 0.14–1.06.

The primary analysis detailed in Section 4.4 proposes the first hypothesis test for CDR-SB be a comparison between a single pooled 4500 mg and 8100 mg dose arm versus placebo (pre-dropout n = 228 and 137, respectively). Assuming a true 0.6-point difference in mean CDR-SB decline between the pooled MTAU9937A arm and placebo at Week 73 (a 40% relative reduction in decline versus placebo), a standard deviation across patients of 2, and a 25% dropout rate, this hypothesis test is expected to have 68% power at the alpha = 0.05 level.

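### Making the formal 8100 mg test wait for a significant 4500 mg result is not needed for primary-endpoint error control, and costs about 10 points of power for 8100 mg

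*SAP*

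**What the plan says.** SAP 4.4 (Type I Error Management) states: "Type I error for the primary endpoint will be controlled using a fixed sequence testing procedure at the two-sided 5% significance level". Under Comparisons of Interest, Group 1 is "MTAU9937A 4500 mg + MTAU9937A 8100 mg vs placebo", Group 2 is 4500 mg, Group 3 is 8100 mg and Group 4 is 1500 mg, each against placebo. The pooled comparison comes from its own model; for the rest, "A second model including all 3 active arms separately will be used for Groups 2-4".

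On the order: "The testing procedure will proceed with comparisons following the order across the four dose groups detailed above". On the gate: "each subsequent hypothesis will only be formally tested if the preceding one is significant at the 5% level". So 8100 mg is formally tested only if both the pooled test and the 4500 mg test are significant, and 1500 mg only if all three earlier tests are.

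Each dose group that succeeds on CDR-SB opens its own sequence of four secondary endpoints at 5%, with no correction across groups. SAP 4.4.1 reports every arm's difference from placebo with a 95% confidence interval, whatever the gate decides. SAP 2.2 states power for the pooled test only (68%). The SAP gives no reason for placing 4500 mg before 8100 mg.

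**The concern.** A gate in a testing hierarchy normally pays for itself by protecting the error rate. Here the pooled test, placed first, already protects the pair of doses inside it, so a second gate between those two doses looks redundant.

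At stake is one pattern of results: the pooled test and the 8100 mg comparison are both significant, but 4500 mg misses 5%. The plan then allows no formal 8100 mg claim and leaves that dose's secondary sequence closed. Protocol 3.3.1 says that the efficacious dose is unknown and that three doses are studied "in order to explore dose/exposure-response relationships for efficacy". A formal high-dose claim that depends on the middle dose sits awkwardly with that aim.

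**Working it through.** **Inputs.** From SAP 2.2: 457 patients, SD 2, 25% dropout, a 0.6-point effect for the pooled arm, and "pre-dropout n = 228 and 137, respectively" for the pooled and placebo groups. From SAP 3.1: allocation 2:3:2:3. Completers per arm are 457 × share × 0.75, which gives placebo 102.8, 4500 mg 102.8, 8100 mg 68.6 and 1500 mg 68.6. The MMRM is approximated by a comparison of normal means with known SD.

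**The plan's own figures.** For the pooled test, SE = 2 × √(1/102.8 + 1/171.4) = 0.2495 and 0.6/0.2495 = 2.405. Power is Φ(2.405 − 1.960) = 67%, against 68% stated. For 4500 mg alone, SE = 2 × √(2/102.8) = 0.2789, and 0.6 ± 1.645 × 0.2789 gives 0.14 to 1.06, the SAP's 90% interval. Both reproduce.

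**Is the inner gate needed?** Consider the alternative rule: pooled test first; if significant, 4500 mg and 8100 mg each at 5%; 1500 mg only if both succeed.

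- Pooled null true (neither dose works, or opposite effects cancel): every false claim must first pass the pooled test, so the error is at most 5%.
- Pooled null false, 4500 mg null: 8100 mg must then have an effect. A false claim needs 4500 mg to be rejected, and a false 1500 mg claim also requires that rejection. At most 5%.
- Pooled null false, 8100 mg null: the same argument applies through the 8100 mg test. At most 5%.
- Both doses effective and the pooled null false: only 1500 mg can be claimed falsely, in one 5% test.

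These cases are exhaustive, so the alternative has strong 5% control on CDR-SB. Simulation over a grid of true effects (4,000,000 draws, shared placebo arm, pooled mean weighted by arm size) gave a maximum familywise error of 5.0% for both rules.

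**What the gate costs.** For 8100 mg alone, SE = 2 × √(1/102.8 + 1/68.6) = 0.3119. Simulated probability of a formal 8100 mg claim:

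| True effect, 4500 / 8100 mg | SAP order | Without inner gate |
|---|---|---|
| 0.6 / 0.6 | 35% | 45% |
| 0.45 / 0.6 | 25% | 41% |
| 0.4 / 0.8 | 27% | 57% |
| 0.3 / 0.9 | 18% | 57% |
| 0 / 0.6 | 2% | 15% |

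The first row applies the SAP's planning effect to each dose. The other rows are illustrative assumptions and are not in the documents. The gap between the columns is the probability of the problem pattern. In the first row it is 45.3 − 35.1 = 10.2 points, or 10.2/45.3, a little over a fifth of the trials in which the pooled and 8100 mg tests both succeed. At 0.6 in every arm, power is the same under both rules for the pooled test (67%), 4500 mg (54%) and 1500 mg (24%).

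**What changes for the worse.** With effects 0.6/0/0 (4500/8100/1500 mg), actual primary-endpoint error rises from 2.3% to 2.5%, still within 5%. The 8100 mg secondary sequence also opens more often. Taking the first secondary endpoint as null in all groups and independent of CDR-SB (an assumption), with a very strong 8100 mg effect (3 points) and the other doses null, error over primary plus first secondary rises from 9.6% to 12.2%. With strong effects at both 4500 and 8100 mg it is about 14% under either rule.

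**The case against.** The strongest reply is that nothing here is invalid. A fixed sequence at two-sided 5% protects the primary endpoint, and 4500 mg is a natural dose to test early. It has the larger allocation, it is the dose in the precision calculations (Protocol 6.1, SAP 2.2), and it is the only dose in the open-label extension and the only active dose in the companion study in moderate disease (Protocol 1.2.2). All of that stands. It explains why 4500 mg is listed first, but it does not show that 8100 mg must wait for it once the pooled test has passed.

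Three stronger readings are tempting, and the documents do not support them.

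- A reader might infer that the lost 8100 mg claim is a likely outcome. Under the only effect the SAP states, applied to both doses, its probability is about 10%. The gaps of 30 points and more need dose slopes that appear nowhere, and Protocol 3.3.1 predicts target engagement above 80% at all three doses, while noting that the engagement needed for efficacy is unknown.
- A reader might infer that the gate has no effect at all on error. It leaves the guaranteed primary-endpoint level unchanged, but it does incidentally limit how often the 8100 mg secondary sequence opens. The SAP claims no control across those sequences, so this does not invalidate the change, but it should be disclosed.
- A reader might infer that the 8100 mg evidence is lost. The estimate and its 95% interval are reported either way (SAP 4.4.1), which for a Phase II proof-of-concept trial is much of the value. What is lost is the formal claim and its secondary sequence.

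**Conclusion.** The point holds as a matter of efficiency. The SAP's sequence controls primary-endpoint type I error correctly. The inner gate from 4500 mg to 8100 mg is not required for that control and lowers the chance of a formal 8100 mg claim from about 45% to 35%, with 0.6 points at both doses. Whether to pool is a matter of judgement. Given the pooled first test, the side-by-side rule keeps every primary-endpoint claim the plan allows and adds some, at the same guaranteed level.

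The 10-point figure rests on arm sizes taken from the allocation ratio, equal 25% dropout, SD 2 and a normal approximation to the MMRM. Larger losses depend on assumed dose slopes. This is a cheap improvement, not a correction of an error.

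**What to change.** Before the unblinding described in SAP 2.3, replace the ordering paragraph in SAP 4.4 with:

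1. Test Group 1 (pooled) at two-sided 5%.
2. If it is significant, test Group 2 (4500 mg) and Group 3 (8100 mg), each at two-sided 5%, neither conditional on the other.
3. Test Group 4 (1500 mg) at two-sided 5% only if Groups 2 and 3 are both significant, which is the present condition.

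Step 3 must keep both conditions. If 1500 mg followed 8100 mg alone, the primary-endpoint familywise error would reach about 9% when 8100 mg is strongly effective and the other two doses are null.

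Add a sentence saying that familywise control applies to the primary endpoint, and that the secondary sequences are not controlled across dose groups. The cost is one paragraph of SAP text. It needs no extra patients, loses no power for any primary-endpoint test and leaves the guaranteed 5% primary-endpoint level as it is. The price is the small rise in actual error within that limit and the more frequent opening of the 8100 mg secondary sequence.

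### Does opening a separate 5% secondary sequence in each winning dose group leave secondary claims uncontrolled across doses?

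*SAP*

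**What the plan says.** SAP section 4.4 sets out the comparisons: "Thus, there will be four comparisons across the doses". They are 4500 and 8100 mg pooled, 4500 mg, 8100 mg and 1500 mg, each against the same placebo arm. One model serves the pooled test; for the rest, "A second model including all 3 active arms separately will be used for Groups 2-4".

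Under the Type I Error Management heading, the primary rule is "Type I error for the primary endpoint will be controlled using a fixed sequence testing procedure at the two-sided 5% significance level", with the condition that "each subsequent hypothesis will only be formally tested if the preceding one is significant at the 5% level". The secondary rule is that, for a dose group that wins on CDR-SB, "a separate fixed sequence testing procedure will be ungated for that dose group's secondary endpoints that will similarly proceed at the 5% level". The accompanying table lists the secondary order (ADAS-Cog13, ADCS-ADL, RBANS, Amsterdam iADL), with arrows running down each dose-group column.

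The section closes with "No control for type I error will be applied for the exploratory endpoints, including sensitivity, subgroup, and biomarker analyses". No sentence states over which family of tests the secondary error is held at 5%. Protocol section 6.4.2 says only that secondary endpoints are analysed like the primary and gives no multiplicity rule.

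**The concern.** After a CDR-SB win, the full 5% passes to the next dose group's CDR-SB test, and the same 5% opens that group's secondary sequence. The level is used twice. Nothing is split or passed between the columns at the secondary level, so as many as four secondary sequences can each run at 5%.

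The placement adds to the worry. The secondary sequences sit under a heading about type I error, and only exploratory endpoints are listed as uncontrolled. A reader might infer that the whole table of secondary claims is protected at 5%. The excess also grows with success: the larger the CDR-SB effect, the more columns open, and that is when secondary claims would be made. A single significant ADAS-Cog13 result at one dose could then be given more weight than its error rate supports.

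**Working it through.** **Inputs from SAP section 2.2.** "This study enrolled 457 patients randomized to one of three active IV dose arms or to an IV placebo dose arm in a 2:3:2:3 ratio", which is about 91, 137, 91 and 137 patients for 1500 mg, 4500 mg, 8100 mg and placebo. SD 2, dropout 25%, effect 0.6 points. The effect is stated for the 4500 mg arm and, for power, as follows: "Assuming a true 0.6-point difference in mean CDR-SB decline between the pooled MTAU9937A arm and placebo at Week 73". No effect is stated for 1500 mg.

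**Reproducing the plan's figures.**
- Pooled test: 228 × 0.75 = 171 active, 137 × 0.75 = 102.75 placebo. SE = 2 × √(1/171 + 1/102.75) = 0.250. Then 0.6/0.250 = 2.40, and power = Φ(2.40 − 1.96) = 67%, against a stated 68%.
- 90% interval for 4500 mg: SE = 2 × √(2/102.75) = 0.279, and 0.6 ± 1.645 × 0.279 = 0.14 to 1.06, as stated.

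**Correlation between the four comparisons.** They share placebo, and Group 1 is a weighted mean of the 4500 and 8100 mg arms. With variances proportional to 1/0.3 (placebo, 4500 mg) and 1/0.2 (1500 mg, 8100 mg), the correlations are:

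| Pair | Correlation |
|---|---|
| Groups 1 and 2 | 0.89 |
| Groups 1 and 3 | 0.80 |
| Groups 1 and 4 | 0.50 |
| Groups 2 and 3 | 0.45 |
| Groups 2 and 4 | 0.45 |
| Groups 3 and 4 | 0.40 |

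**Error when a fixed number of secondary sequences is open.** With ADAS-Cog13 null in every arm, simulation of these correlated statistics gives the chance of at least one false rejection as 5.0%, 7.1%, 9.9% and 13.6% for one, two, three and four sequences. Four independent tests would give 1 − 0.95⁴ = 18.5%.

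**Error over the whole procedure at the planning effect.** Weight those rates by the chance that exactly that many sequences open. This is exact when CDR-SB and ADAS-Cog13 are uncorrelated.

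- 0.6 points in all three active arms. Gates open with probability 67.1%, 54.3%, 35.2% and 24.2%, so exactly one to four are open with probability 12.8%, 19.1%, 11.0% and 24.2%. Error = 0.128 × 5.0 + 0.191 × 7.1 + 0.110 × 9.9 + 0.242 × 13.6 = 6.4%.
- 0.6 points in 4500 and 8100 mg, none in 1500 mg. Gates open with probability 67.2%, 54.4%, 35.2% and 2.1%, so exactly one to four are open with probability 12.8%, 19.2%, 33.1% and 2.1%. Error = 0.128 × 5.0 + 0.192 × 7.1 + 0.331 × 9.9 + 0.021 × 13.6 = 5.6%.

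The documents give no correlation between the two endpoints, so a range is assumed. The simulated two-sided rates are:

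| Assumed correlation | 0.6 in all active arms | 0.6 in 4500 and 8100 mg only |
|---|---|---|
| 0 | 6.4% | 5.6% |
| 0.3 | 6.2% | 5.4% |
| 0.5 | 6.0% | 5.3% |
| 0.7 | 5.8% | 5.2% |

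The 13.6% figure holds when all four gates are certain to open, or when all four are open and the endpoints are uncorrelated. Conditioning on four actual wins at 0.6 points in every arm gives 13.6-17.3% over the same correlation range. That conditioning event has probability 24%, or about 2% if 1500 mg has no effect.

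**Price of cross-dose control.** Bonferroni over four sequences is 1.25% each (critical value 2.498) and gives 3.7% with all four open. At a standardised effect of 0.3 (assumed for the secondary; it equals 0.6/2), first-step power falls as follows:
- Group 1: Φ(2.403 − 1.960) = 67% to Φ(2.403 − 2.498) = 46%.
- Group 2: Φ(2.150 − 1.960) = 58% to Φ(2.150 − 2.498) = 36%.
- Group 3: Φ(1.921 − 1.960) = 48% to Φ(1.921 − 2.498) = 28%.

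**The case for a change.** The strongest case for a change is that one added sentence, saying that secondary tests are controlled within a dose group and nominal across groups, would cost no power and would prevent over-reading. The excess is also not always small. At assumed CDR-SB effects of 0.8 and 1.0 points in every arm, the cross-dose rate is 7.6-9.9% and 10.0-12.2%. Counting only false claims of benefit, against a nominal 2.5%, the rate is 3.2-5.6% at 0.6 points in all arms and 2.8-4.9% with no 1500 mg effect.

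What stands is that the SAP neither claims nor disclaims cross-dose control of the secondary endpoints. What does not stand is that a reader is misled. The text names control for the primary endpoint only, calls each secondary sequence separate, ties it to its own dose group, and draws the arrows down the columns. The inference that everything outside the exploratory list must be controlled across doses is an argument from silence. The sentence would be harmless, but it would alter no test, threshold or result. The larger effects of 0.8 and 1.0 points appear nowhere in the documents.

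**Conclusion.** No change follows. Secondary claims are controlled at 5% within a dose group and not across dose groups. That is the natural reading of SAP section 4.4, and an analyst reporting the results would present them dose by dose. CDR-SB error is unaffected.

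At the effect the SAP states, the two-sided excess over 5% is 0.2-0.6 percentage points if 1500 mg has no effect and 0.8-1.4 points if it shares the 0.6-point effect. These sizes assume ADAS-Cog13 null in every arm while CDR-SB works in at least two, an endpoint correlation of 0 to 0.7, SD 2 and 25% dropout.

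Buying cross-dose control at 1.25% per sequence would cost 20 to 21 points of power on the first-step secondary tests of Groups 1 to 3, and would still not hold the combined primary and secondary error at 5%. Protocol section 1.4 describes a proof-of-concept study, section 3.3.1 says three doses are studied to explore dose response, and section 6.1 justifies the sample size by precision. In that setting the dose-by-dose scheme is a fair trade-off. The unstated scope is a missing detail that readers can fill from the text.
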